7. STUDY POPULATION AND RECRUITMENT

Describe who and how many subjects will be invited to participate. Include age, gender and other pertinent information.

For this study, a total of 180 community-dwelling older adults (aged 60-85) with chronic low back pain (LBP) will participate. In addition to having a primary complaint of chronic LBP, participants must also have co-existing hip weakness and hip pain.

Participants will be recruited from one of three regions: Newark, DE and surrounding communities, Pittsburgh, PA and surrounding communities and Durham, NC and surrounding communities.

Inclusion Criteria

- (a) Low Back Pain for at least 3 months with LBP being an ongoing problem for at least half the days in the past 6 months. The NIH Research Task Force on Chronic LBP (RTF) established this as the definition of chronic LBP for future trials.^{43,83} A patient with pain on at least half the days in the past 6 months would have accumulated at least 3 months' worth of pain days, and the Task Force concluded that this would be the recommended definition for 'chronic' pain.
- (b) At least moderate pain intensity (> 3 on a scale of 0 (no pain) to 10 (worst pain imaginable), which has been shown to be significant in the pain literature, is required to ensure our ability to detect treatment effects.
- (c) Classified into the "weak+painful" hip-spine subgroup: Participants must have hip internal rotation strength (normalized to body weight) that is less than .26 and a HOOS raw score on pain items P4-P8 less than 15. In our previous sample of 250 older adults with low back pain, we found that 41% met these criteria.
- (d) Age: Age range (60-85) was selected to permit study of the effect of the intervention on a representative sample of community-dwelling older adults. While individuals < age 60 often suffer from chronic LBP, little is known about how to intervene for those \geq age 60. Thus, we will focus on older adults in the proposed study.
- (e) Fluent in speaking and reading English: Community-dwelling older adults who are only fluent in other languages will not be included because of the lack of feasibility of employing reliable instruments and interviewers fluent in other languages.

Attach all recruitment fliers, letters, or other recruitment materials to be used. If verbal recruitment will be used, please attach a script.

Participants will be recruited through print advertisements posted in local newspapers, newsletters, senior centers, and online. We will also recruit participants with low back pain who have participated in prior research and signed a 'consent-to-be-recontacted' form.

Recruitment materials, including the verbal script, have been uploaded with the package.

Describe what exclusionary criteria, if any will be applied.

Exclusion Criteria

Participants will not be eligible for participation if he/she has:

- a. Significant pain in the legs greater than the back or acute LBP: Since we will be specifically evaluating chronic LBP and its impact on function, we do not want to confound the outcome data with prominent pain from the legs; it is unlikely that pain in the shoulder, neck, or upper body will affect functional testing, therefore, there is no need to exclude these individuals with pain in these areas. Thus, only individuals with LBP severity greater than pain severity in the lower extremity will be included.
- b. Known spinal pathology other than osteoarthritis: (e.g., a history of back surgery or recent trauma within the past 6 months, vertebral fractures within the past year, ankylosing spondylitis, carcinoma metastatic to the spine). In these other cases, LBP may be of non-mechanical origin and non-responsive to the proposed interventions.
- c. Previous hip fracture repair, hip fracture without repair in last 15 years, or total hip replacement: These are confounding variables that may impact patient prognosis.
- d. Non-ambulatory, or severely impaired mobility (i.e., require the use of an assistive device greater than a cane): Since functional performance measures in the proposed study includes gait speed and standing balance, conditions other than LBP that could negatively impact these measures may confound our study results.
- e. Severe visual or hearing impairment: Since this study will involve questionnaires, telephone evaluations, and onsite evaluations, severe visual and/or hearing impairments may interfere with data collections
- f. Current infection/illnesses that would affect participation, recent hospitalization in past 3 months, or abnormal blood pressure: To insure weekly participation and a six month follow-up, potential participants with an acute infection/illness or who are recovering from a recent hospitalization will be excluded from the study. Those who fail the blood pressure screen due to abnormal readings at the initial evaluation will also be excluded and referred to their primary care practitioner.
- g. Received manual therapy or exercise therapy (e.g. physical therapy, chiropractic care) for the low back or hip within in the last 3 months: This is to ensure a “washout” period whereas changes in participant status are likely to occur from the proposed treatment intervention rather than a prior intervention.
- h. Inability to participate in the study for the full six months for any known reason (i.e. moving, extended vacation, planned surgery): This is an effort to ensure participants receive the intervention as directed and to retain participants over the course of the study.
- i. Folstein Mini-Mental State Examination score of <24^{62,63}: Individuals will be excluded because of the uncertain reliability of their answers to the self-reported outcome measures.
- j. Red flags indicative of a serious disorder underlying their LBP: Red flags that would require specialized medical attention include fever associated with LBP, significant unintentional weight loss (>10 pounds), trauma that preceded the onset of LBP, night pain that is unrelenting and particularly bothersome, or signs and symptoms of cauda equinae (i.e. loss of sensation over

saddle region, significant disturbances in bowel and bladder function, which are potentially related to low back pain). These individuals will be promptly referred to their primary practitioners.

Describe what (if any) conditions will result in PI termination of subject participation.

Termination of the initial evaluation may occur if after the participant has signed the informed consent form, it is determined during the course of the initial onsite evaluation that he/she does not meet study eligibility criteria (e.g. screening criteria, abnormal blood pressure $\geq 180/110\text{mmHg}$, <24 on mental screen, insufficient hip internal rotation strength deficit). PI termination of subject participation, otherwise, would only occur under a circumstance in which it became clear that the participant could not participate in a safe manner. At this time, there is no foreseeable risk that we could identify that would lead to termination from study participation, although we acknowledge that certain situations may require modification of treatment approach (e.g. increase in LBP or hip pain) or modification of the re-evaluation (e.g. abnormal blood pressure).

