While there is longstanding expert agreement that LBP patients should be classified into subgroups prior to treatment,¹⁸⁻²⁰ no classification systems specific to the geriatric LBP population have been developed. There is strong evidence that classification approaches, where treatments are matched to the patient's limitations of that specific sub-group, can improve outcomes for patients undergoing physical therapy treatment for LBP.²¹⁻²⁴ To develop effective treatments, we must develop appropriate classification systems for older adults with chronic LBP.

Our preliminary data from the initial testing of the proposed hip-focused treatment among older adults with LBP suggest that this LBP subgroup may have a more favorable treatment response when the identified hip deficits, i.e. limitations, are also addressed. Therefore, the natural next step is to refine and further explore this hip-focused treatment for this newly identified at-risk subgroup (i.e. those with hip pain and weakness) through a well-controlled clinical trial. We propose a multi-site, single-blinded (i.e. examiners will not know participant treatment group assignment), randomized-controlled (i.e. participants will have an equal chance of getting 1 of 2 treatment plans), trial that advances findings from our previous study. We will recruit a total of 180 older adults with LBP of at least 3 months duration (i.e. chronic LBP) who are classified as members of the at-risk hip-spine subgroup. We will investigate whether a hip-focused treatment plan warrants further investigation as an approach to improve LBP and outcomes among older adults with chronic LBP. Manual therapy techniques will be used to address hip joint pain and progressive strengthening will be used to address hip weakness in one treatment group as compared to a LBP-focused treatment including manual therapy techniques to the low back region and low back muscle stretching. We will measure disability, LBP intensity, physical function (i.e. walking speed, chair rise performance, balance) and clinical hip deficits at baseline and after 8 weeks of intervention. We will also do a follow-up at 6 months (16 weeks post-treatment) to assess whether improvements hold from post-treatment to 4 months post-treatment.

The goals, i.e. specific aims, of the proposed research are to:

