1. Explore whether a hip-focused treatment leads to reduced disability and improved physical function when compared to a low back-focused treatment in an at-risk hip-spine subgroup (i.e. those with both hip pain and weakness, in addition to low back pain).
2. Determine what contributes to improvements in disability and physical function in this at-risk hip-spine subgroup.

6. PROCEDURES Describe all procedures involving human subjects for this protocol. Include copies of all surveys and research measures.

Study Participants.

Participants with moderately intense (LBP rated at least 4/10), chronic LBP (pain of at least 3 months) that impacts daily activities with concurrent hip pain and hip weakness will be recruited from newspaper and online advertisements, as well as from databases of former study participants who have agreed to be contacted for future studies. The sample will be recruited from one of three areas in this multi-site clinical trial: Newark, DE and surrounding communities, Pittsburgh, PA and surrounding communities and Durham, NC and surrounding communities.

Design and Randomization Plan.

In total, 180 participants meeting the inclusion/exclusion criteria will be randomly assigned into one of two intervention groups: (1) spine treatment supplemented with a hip-focused manual therapy and hip-focused exercise intervention, or (2) spine-focused rehabilitation with stationary cycling. We will use statistical software to generate a randomization plan that ensures by the end of the study that an equal number of participants are randomly assigned to each of the two treatment conditions. We will perform randomization separately in men and women given the reported sex differences in pain conditions among older adults²⁵, this approach will ensure equal randomization of men and women into both randomization groups. The treatment assignments will be uploaded into the web-based data entry application for the study. A participant's study allocation will be revealed to approved study personnel (i.e. not physical therapy testers) once all eligibility criteria have been entered and eligibility is confirmed.

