The manual therapy intervention is based on the protocols used by Hoeksma and colleagues^{76,77} which have demonstrated efficacy in the treatment of primary hip osteoarthritis. Treatment will be delivered to both hips. The following techniques will be applied: (a) supine long-axis distraction manipulation in flexion, abduction and internal rotation; (b) supine anteroposterior hip mobilization with hip and knee flexed; (c) prone posteroanterior hip mobilization, and (d) lateral femoral glide with internal rotation using belt. For technique (a), the PT performs 3 sets of sustained stretches for 30 seconds followed by traction manipulations. For techniques (b-d), the PT performs 3 sets of grade III-IV joint mobilizations for a duration of 30 seconds/set. Mobilizations will be followed with manual stretching of the hamstrings and hip flexors by the physical therapist.

The hip strengthening intervention will include a progressive protocol focused on isolated strengthening of the hip abductor, extensor internal and external rotator muscles, as well as a functional hip training component. The progressive strengthening component will use elastic tubing and is based on the work of Khayambashi et al,⁷⁸ which resulted in hip strength gains from 32-56%. In our preliminary evaluation of the hip intervention in a UD clinical pilot trial, we saw a signal for improvement in gait speed (+.07m/s), but it was not as strong as the changes in pain. Therefore, we added a functional hip progression, including mobility-focused hip exercises, which we anticipate will transfer into greater performance-based mobility gains. See Table 2 for an overview of the hip exercise program.

Functional Hip Exercises

Table 2. Standardized Hip Strengthening Progression				Functional Hip Exercises
Weeks	Set 1* (12)	Set 2* (12)	Set 3* (12)	
1-2	Yellow	Yellow	Red	[Done with appropriate guarding by licensed PT.]
3-4	Red	Red	Green	High Step Marching (2 minutes), Side Stepping in both directions (2 minutes), Forward Step-Ups (3 sets, 12 repetitions)
5-6	Green	Green	Blue	Forward Band Walking (2 minutes), Side Band Walking(2 minutes), Lateral Step-Ups (3 sets, 12 repetitions)
7-8	Blue	Blue	Black	

*Values are band color, indicating resistance level. Yellow offers the lowest resistance (3 pounds) and Black is the highest resistance in this sequence (7.3 pounds). The number of repetitions is given in parentheses for each set.

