The trunk muscle training (TMT) program, which was recently used by the principal investigator in a randomized clinical trial⁷⁹ among older adults with chronic LBP, is based on evidence from the biomechanical and electromyography studies done by McGill et al⁸⁰. The following muscle groups have been identified in the literature as primary active stabilizers of the trunk: rectus abdominus, transversus abdominus, oblique abdominals, multifidus and erector spinae (see Table 3). The goal of this stabilization program is to increase muscle stiffness and thereby create sufficient stability in the spine through motor control system re-education. The treating PT progresses each patient through the same criterion-based program as each individual patient achieves the specific goals. For each exercise, the goal is that the participant will perform at least 30 repetitions before they can progress to the next exercise in the group. Once achieved, he or she is allowed to progress to the next exercise. With this criterion-based program, if the patient immediately could meet a specific requirement, then he or she could advance to the next exercise. At each exercise session, the participant will perform at least one exercise from each of the targeted muscle groups.

Table 3. Overview of Trunk Muscle Training Program

Muscle	Importance of Muscle	Examples of Exercise Progression
Transversus Abdominus (TrA)	
 Draws in abdominal wall TrA may activate in a feed-forward mechanism to stabilize the trunk for extremity motions 	Abdominal Bracing in supine>> Bracing in hook-lying with arm movements>> Abdominal Bracing in standing Possible Substitutions: holding breath
Erector Spinae/ Multifidus	
 Extend the spine Segmental extensors co-contract with anterolateral abdominals to stabilize trunk 	Single arm lifts-standing while leaning with elbows resting on countertop>> Single arm lifts-prone over bolster>> Progress to quadruped with arm lift
Rectus Abdominus	
 Primary flexor of the trunk 	Curl ups as described by McGill-- maintain neutral spine & avoid excessive trunk flexion
Oblique Abdominals	
 Co-contracts with multifidus for trunk stabilization, generates side-bending and rotation forces in 	Same as above for transversus abdominus

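### People given the hip-focused treatment in the team's pilot can be recruited again after a 3-month washout and randomised to the spine-focused arm, which would modestly dilute the treatment difference

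*Combined protocol and SAP*

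**What the plan says.** Section 6 (Study Participants) recruits through advertisements, "as well as from databases of former study participants who have agreed to be contacted for future studies". Section 7 repeats the route: "We will also recruit participants with low back pain who have participated in prior research and signed a 'consent-to-be-recontacted' form".

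Section 5 reports preliminary data from first testing of the hip-focused treatment in older adults with LBP. Section 6 (Group 1) places that work at the lead site, introducing a gait-speed result with the words "In our preliminary evaluation of the hip intervention in a UD clinical pilot trial". The same paragraph says that a functional hip progression was added afterwards, so the pilot package was an earlier version of the present one.

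The exclusion criterion on earlier therapy is (g): "Received manual therapy or exercise therapy (e.g. physical therapy, chiropractic care) for the low back or hip within in the last 3 months". Its stated reason is: "This is to ensure a “washout” period whereas changes in participant status are likely to occur from the proposed treatment intervention rather than a prior" one. None of the other exclusions, (a) to (f) and (h) to (j), refers to having taken part in the pilot or received the hip programme.

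Section 6 (Group 2) omits the oblique abdominal exercises from SFR because they might also address hip weakness. Section 10 (Statistical Analysis) lists the baseline characteristics to be compared (analgesic use, age, comorbidities, body mass index, gender, race/ethnicity) and adjusts the mixed model for site and sex. Prior exposure to the study treatment is in neither list.

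**The concern.** The comparison is meant to isolate what hip-focused treatment adds. The plan takes some trouble over this and removes even trunk exercises that might train the hip from the comparator. Yet someone who completed the team's own hip programme, and took home what it taught, can be randomised to that comparator once three months have passed. This exposure would be larger than the one the plan designs out.

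Previously treated people may show a smaller HIP+ versus SFR difference than people new to the hip programme. The estimated effect would then shrink towards zero in proportion to their share. As prior exposure is not a listed baseline variable or covariate, the report might not show how many such people there were or how they fell between the arms.

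**Working it through.** **Can such a person enrol?** Setting the sections side by side:

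1. Recruitment source: former study participants with LBP (sections 6 and 7).
2. Earlier delivery: the hip treatment was given in a pilot at the lead site (section 6, Group 1), in older adults with LBP (section 5).
3. Bar on earlier treatment: only the 3-month rule in exclusion (g).
4. Other filters: inclusion (a) to (c) require back pain on at least half the days over six months, pain above 3 out of 10, and current hip weakness and hip pain.

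A pilot participant treated more than three months ago who still meets (a) to (c) is therefore eligible. The documents do not say that the databases hold pilot participants; they leave it open.

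**How large could the dilution be?** The plan has no figure to reproduce: it gives N = 180 but no target effect, standard deviation, power or dropout allowance. The following is illustration only.

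Inputs from the documents: 180 participants allocated equally, so 180 / 2 = 90 per arm; two-sided alpha 0.05.

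Assumptions: no dropout; 80% power before dilution; a fraction f of each arm previously exposed; these people retain a share r of the between-arm effect.

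- Detectable standardised difference: d = (1.960 + 0.842) × √(2/90) = 0.418.
- Diluted difference: d′ = d × [1 − f(1 − r)].
- Power: Φ(d′ × √(90/2) − 1.960).
- Number per arm to restore 80%: 90 / [1 − f(1 − r)]², rounded up.

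| f (people of 180) | r | d′ | Power | n per arm for 80% |
|---|---|---|---|---|
| 5% (9) | 0 | 0.397 | 76% | 100 |
| 5% (9) | 0.5 | 0.407 | 78% | 95 |
| 10% (18) | 0 | 0.376 | 71% | 112 |
| 10% (18) | 0.5 | 0.397 | 76% | 100 |

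Worked line for f = 10%, r = 0: d′ = 0.418 × 0.90 = 0.376; 0.376 × 6.708 − 1.960 = 0.56; Φ(0.56) = 0.71.

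The proportional loss of effect is f(1 − r): 10% in that line and 2.5% in the mildest one. It does not depend on the assumed power.

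**The case against.** The strongest reply is that inclusion (a) to (c) already do much of the work. The six-month look-back, the pain threshold and the hip criteria tend to screen out anyone with substantial lasting benefit. Any stable residual benefit is also in the baseline measurement, randomisation spreads prior exposure across arms on average, and the pilot took place at one of three sites without the functional progression. The pilot is undated, but its results were known in time to reshape the treatment. Someone who had ordinary hip therapy elsewhere four months ago stays eligible too. Finally, the telephone questionnaire and recruitment script are not among the documents, so a question on prior participation may already exist.

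Most of this stands, and it is why the point is modest. It does not close the gap. The entry criteria limit carry-over of benefit but may select people who did not respond to the hip treatment before. Ordinary therapy varies in content and is hard to verify, whereas the team can identify exactly who received its own programme.

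A reader might also infer several stronger things that the documents do not support:

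- **That the comparison is confounded.** Exposure precedes randomisation, so what is expected is dilution. A chance imbalance is possible, but it is not systematic bias.
- **That the washout is shown to be too short because follow-up runs to 16 weeks after treatment.** Testing whether gains persist does not assert that they do.
- **That participants in the earlier trunk training trial should be barred too.** That programme, "which was recently used by the principal investigator in a randomized clinical trial", is given in both arms here (without the oblique exercises in SFR), so prior exposure does not bring hip treatment into SFR. The trial report is dated 2016 (reference 79), and the safety board approved this protocol in August 2019, before enrolment.
- **That returning participants compromise blinding.** Section 5 describes only the examiners as unaware of allocation; participants are not masked in any case.
- **That the 6-month contrast suffers most.** Nothing in the documents allows this to be derived.

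**Conclusion.** The concern holds in a limited form. As written, the plan allows people who received the team's hip-focused treatment to be recontacted, to pass the 3-month rule and to be randomised to a comparator deliberately kept free of hip training. It does not provide for showing this in the baseline comparison or adjusting for it in the model.

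The expected consequence is a small dilution of the HIP+ versus SFR difference. With 5% to 10% exposed, power falls from an assumed 80% to about 76% to 71% if exposed people show no between-arm difference, or to 78% to 76% if they keep half of it. These figures rest on assumed values of f and r, no dropout and a simple two-sample calculation. If no pilot participant is in the recontact databases, the loss is zero. This is a cheap improvement to the design and does not put the trial's validity in doubt.

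**What to change.** Add to the exclusion criteria prior receipt of the hip-focused intervention in this team's pilot, whatever the date, and check candidates against the pilot roster before recontact. Former participants who did not receive that intervention stay eligible, including those from the trunk training trial. If the roster shows no overlap with the recontact databases, one sentence saying so settles the matter.

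If anyone so exposed is already enrolled, keep them in the intention-to-treat analysis, record the exposure, report it by arm, and pre-specify a sensitivity analysis without them. Because the exposure precedes randomisation, the remaining participants still form a randomised comparison.

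The cost is one eligibility line and one roster check. The downside is the loss of a few easily reached candidates.
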